7.3 Center Pooling

The ArcticLine Feasibility study is expected to be conducted at 4 centers in the US and Canada, with a total enrollment of up to 45 subjects to ensure the treatment of at least 15 subjects with the ArcticLine catheter.

The observed rate of the primary endpoint is expected to be low (10% or less, which would lead to an expected outcome of 1 or 2 subjects with primary safety events), so a formal assessment of site-to-site heterogeneity of outcomes in a sample of 15 subjects apportioned between 4 centers is exceedingly

unlikely to detect a difference. As such, any assessment of differences in outcomes between sites and other subgroupings will be qualitative in nature. Data from all sites will be combined without regard to center location for the analysis of the study's endpoints.

7.4 Handling of Missing, Unused, and Spurious Data and Dropouts

Subjects who (A) exit the study prior to completion of a phone conversation or follow-up visit 7 or more days after the index procedure and (B) do not have a primary safety event on or before discharge from the index ablation will be considered as missing for the primary endpoint analysis, on grounds that the assessment of the endpoint is incomplete. Subjects with early exits occurring after the one-week phone call will still be included, however: after 7 days post-index ablation, only the atrioesophageal fistula component, which occurs in less than one in 10,000 cryoballoon ablations¹, counts toward the primary endpoint. Therefore, the likely impact of failing to observe new occurrences of the primary endpoint in subjects not followed past one week is negligible. No effort to statistically impute missing data will be made for the primary endpoint or any ancillary endpoints; all such analyses will be "complete cases" and assume that observed missingness occurs completely at random with respect to the outcome.

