8.8.4. Unscheduled Office Visits

An unscheduled visit is defined as any unplanned cardiovascular-related office visit or early study exit at the study center that occurs between CIP required visits. If the subject exits the study early, an unscheduled office visit should occur. The following information is required to be collected at unscheduled follow-up visits:

- Review medications
- Adverse event assessment
- Review symptoms suggestive of recurrent AF/AT/AFL
- 12 lead ECG

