8.12. Subject Withdrawal or Discontinuation

A subject can withdraw from the study at any time. If the subject wishes to exit early from the study, the center is required to document the reason for exit on an eCRF and in the subject's medical record. In addition, centers shall follow the regulations set forth by their IRB/REB/MEC.

It is recommended that Investigators follow the subject until all device and/or procedure-related adverse events are recovered / resolved or unresolved with no further actions planned. Following completion of the 6 month visit (or after the 6 month visit due CIP v4 follow-up requirements) or early study exit, subjects will continue to receive standard medical care. All data available through the time of the subject's exit will be used for analysis.

Reasons for early study exit include:

- Subject lost to follow-up
- Subject did not meet inclusion/exclusion criteria after consent and did not undergo an ablation procedure
- ArcticLine Catheter was not used during the subject's ablation procedure
- Subject did not provide consent or data use protection authorization
- Subject chooses to withdraw (e.g., consent withdrawal, relocation to another geographic location)
- Investigator deems withdrawal necessary (e.g., medically justified, inclusion/exclusion criteria not met, failure of subject to maintain adequate study compliance)
- The sponsor decides the study will be closed or a particular center will be closed.

In the case that the subject is determined to be lost to follow-up, details of a minimum of two attempts and the method of attempt (e.g., one letter and one phone record or two letters) to contact the subject must be recorded.

An unscheduled office visit should be attempted if the subject exits the study outside of a scheduled follow-up visit. Subjects treated with the ArcticLine Catheter who exit from the study should continue to be followed by an electrophysiologist for follow-up of any potential adverse events at the recommended interval of 6 months from the index ArcticLine Catheter ablation procedure.

For subjects who have not undergone treatment with the ArcticLine Catheter, a new subject may be enrolled to achieve the target sample size of N=15 treated subjects in the Study.

9. Risks and Benefits

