10.3. Reporting of Adverse Events, including Death

For the purposes of the study, all Adverse Events will be collected starting at the time of signing the IC Form through the duration of the subject's participation in the study.

Reporting of these events to Medtronic will occur on an AE eCRF, including a description of AE, date of onset of AE, date of awareness of center, treatment, resolution, assessment of both the seriousness and the relatedness to the investigational device. Each AE must be recorded on a separate AE eCRF. Exceptions include:

- Documented pre-existing conditions are not considered AEs unless the nature or severity of the condition has worsened. Additionally, arrhythmia episodes that are not new or worsening conditions and for which no action is taken are not reportable as AEs.
- Unavoidable Adverse Events, listed in Table 6: Adverse Event and Device Deficiency Definitions need not be reported unless the adverse event worsens or is present outside the stated timeframe after the ablation procedure.
- Cardioversions (DC or Drug) for recurrent symptomatic atrial fibrillation and other atrial arrhythmias are not considered serious adverse events.

Where the definition indicates "device", it refers to any device used in the study. This might be the catheter, or any other component of the system under investigation, or any market-released component of the system.

For any changes in status of a previously reported adverse event (i.e. change in actions taken, change in outcome, change in relatedness), an update to the original AE must be provided. All adverse events must be followed until the adverse event has been resolved, the subject exits the study or until study closure, whichever occurs first.

At the time of study exit, all collected AEs with an outcome of "not recovered/not resolved", "recovering/resolving" or "unknown" must be reviewed and updates provided as applicable.

All reported adverse events will be reviewed by a Medtronic representative. AEs will be classified according to the definitions provided.

Upon receipt of adverse events at Medtronic, a Medtronic representative will review the adverse event for completeness and accuracy and when necessary will request clarification and/or additional information from the Investigator. Medtronic will utilize MedDRA, the Medical Dictionary for Regulatory Activities, to assign a MedDRA term for each adverse event based on the information provided by the Investigator.

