7.2.2 Primary Objective

Estimate the incidence of ArcticLine Catheter-related and ArcticLine cryoablation procedure related Serious Adverse Events (SAEs) with an onset date within 7 days post-procedure.

Endpoint Definition

ArcticLine Catheter-related or ArcticLine cryoablation procedure-related SAEs, with an onset date within 7 days post-procedure (except as noted below), as adjudicated by the Clinical Events Committee (CEC), described as follows:

- Atrioesophageal fistula*

* Includes atrioesophageal fistula with an onset date at any time after the study cryoablation procedure and is adjudicated by the CEC as either ArcticLine Catheter related or ArcticLine cryoablation procedure-related.

- Cardiac perforation/tamponade
- Cerebrovascular accident
- Death
- Esophageal injury
- Major bleeding
- Myocardial infarction
- Pericarditis
- Phrenic nerve injury (ongoing at hospital discharge)
- Transient ischemic attack
- Vagal nerve injury resulting in esophageal dysmotility or gastroparesis
- Vascular access complications

The percentage of catheter related and cryoablation procedure related SAEs will be calculated as the number of procedures with at least one SAE meeting the endpoint definition divided by the number of cryoablation procedures. Exact methods will be used to construct a 95% confidence interval for the percentage of procedures with an SAE.

Each procedure will count towards the primary endpoint, so subjects with repeat ArcticLine ablations will contribute more than once to the denominator.

Sensitivity Analysis: Independence of Primary Events

Note: With version 3 of this SAP, all procedures are complete. No repeat ablations have been or will be performed, so this sensitivity analysis will not be performed.

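### SAP 7.4 sets an observed primary safety event to missing if it begins after discharge and the subject leaves before any contact on day 7 or later

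*SAP*

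**What the plan says.** SAP 7.4 makes a subject missing for the primary endpoint when two conditions both hold. Condition (A) is exit before a phone conversation or visit seven or more days after the index procedure. Condition (B) covers subjects who "do not have a primary safety event on or before discharge from the index ablation will be considered as missing for the primary endpoint" analysis. The reason given is that the endpoint has not been fully assessed. Subjects who exit after the one-week call stay in. Nothing is imputed, and missingness is assumed to be completely at random.

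The endpoint in SAP 7.2.2 takes related, CEC-adjudicated SAEs from a fixed list "with an onset date within 7 days post-procedure (except as noted below"); the exception is atrioesophageal fistula, which counts at any time. The rate is the "number of procedures with at least one SAE meeting the endpoint definition" divided by the number of cryoablation procedures, and all ArcticLine procedures are to be included.

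Three places in the Protocol bear on events between discharge and exit:

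- Section 8.12: "All data available through the time of the subject's exit will be used for analysis".
- Section 10.3: "all Adverse Events will be collected starting at the time of signing the IC Form through the duration" of participation.
- Section 8.8.4: "If the subject exits the study early, an unscheduled office visit should occur"; that visit includes an adverse event assessment.

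**The concern.** Condition (B) looks for events only up to discharge, while the endpoint looks up to day 7. Discharge has no fixed day. Protocol 8.5 places the discharge stroke-scale assessment no earlier than the day after the procedure, so most of the seven-day window can fall after discharge.

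Take a subject who goes home, has a qualifying event on, say, day 4 that the site records and the CEC adjudicates, and who then withdraws before any contact on day 7 or later. Both conditions are met, and the subject disappears from the primary analysis with the event. The exit visit that the Protocol asks for could itself be where the event is found.

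The stated reason does not reach this case. A procedure needs only one qualifying SAE to count, so its outcome is known once one has been observed. The SAP already accepts that logic for events by discharge and gives no reason to stop there.

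The SAP (7.3) expects a low event rate, "which would lead to an expected outcome of 1 or 2 subjects with primary safety events". One lost event would be half or all of the numerator of the primary safety result.

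**Working it through.** **Inputs.**

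- Denominator: 15. SAP 7.7 gives a final cohort of 15, and SAP 7.2.2 notes "No repeat ablations have been or will be performed", so procedures equal subjects.
- Interval: exact (Clopper-Pearson), two-sided 95% (SAP 7.2.2).
- Expected number of subjects with events: 1 or 2 (SAP 7.3).
- Number of affected subjects: not given in the documents. One is assumed for illustration.

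**Formula.** For x events in n, the lower limit is the 2.5% quantile of Beta(x, n − x + 1), or 0 when x = 0. The upper limit is the 97.5% quantile of Beta(x + 1, n − x).

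**Check against the SAP's own figure.** SAP section 6 gives a width of 32% for 1/15. The formula gives 0.17% to 31.95%, width 31.78%, which agrees.

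**Does any other sentence in 7.4 rescue the subject?** No. The only stated inclusion is for exits after the one-week call, and this subject left before it.

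**Effect of the clause with one affected subject.**

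| Other events | SAP 7.4 as written | Cut-off at study exit | Difference |
|---|---|---|---|
| None | 0/14 = 0% (0% to 23.2%) | 1/15 = 6.7% (0.2% to 31.9%) | −6.7 points |
| One, in a retained subject | 1/14 = 7.1% (0.2% to 33.9%) | 2/15 = 13.3% (1.7% to 40.5%) | −6.2 points |

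**Direction.** Dropping a subject with an event turns a/n into (a − 1)/(n − 1). The inequality (a − 1)/(n − 1) ≤ a/n is equivalent to a ≤ n, which always holds. Relative to an exit cut-off, the clause therefore cannot raise the rate.

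**Cost of an exit cut-off.** Event-free early exits are still dropped while early exits with events are kept. Each event-free exit moves 1/15 = 6.7% to 1/14 = 7.1% (+0.5 points), or 2/15 = 13.3% to 2/14 = 14.3% (+1.0 point). The present rule already has this feature for events by discharge.

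**Consistency within one report.** Ancillary Objective 5 tabulates related SAEs through 6 months in all ArcticLine-treated subjects, without this exclusion. In the first row of the table, the primary result would read 0/14 while Ancillary 5 showed at least 1/15.

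**The case against.** The strongest reply is that probably nobody is affected. All procedures were complete when this SAP version was written, and SAP 7.6 presupposes 15 treated subjects with a 1-week visit. A subject with that contact fails condition (A) and is analysed normally. The trigger also needs a conjunction: a listed, serious, related event after discharge, followed by exit before day-7 contact. This stands as a limit on practical effect. It is not proof, because 7.6 states a plan and not attendance.

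Second, the downward direction is relative to an exit cut-off and not to the true rate. Let p1 be the probability of an event by discharge, p2 that of a first event after discharge up to day 7, and e that of early exit. If exit is random, the present rule estimates [p1 + p2(1 − e)]/[1 − e + p1·e]. The numerator of its excess over p1 + p2 is e·p1·(1 − p1 − p2), which is positive when e and p1 are and p1 + p2 < 1. With assumed values p1 = 3%, p2 = 2% and e = 10%, the present rule gives 0.048/0.903 = 5.3% against a true 5.0%. If half of the early leavers' post-discharge events are seen before exit, the exit cut-off gives 0.049/0.904 = 5.4%. The algebra is right, so the change is not a pure bias correction. The case for it is that an observed, adjudicated safety event belongs in the primary safety rate.

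Third, the Protocol leaves data-handling rules to the SAP, and Protocol 8.12 need not mean that every observation enters the primary estimate. That softens the conflict, but the clause still contradicts the SAP's own statement in 7.2.2 that all ArcticLine procedures are included, and its rationale does not apply to a settled outcome.

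Fourth, the event would not be hidden. It would appear in Ancillary 5, in Ancillary 7 if it is on that list, and in regulatory SAE reporting. No hypothesis test or stopping criterion depends on the rate. This bears on severity, not on whether the rule is wrong.

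**Conclusion.** The concern holds. As written, condition (B) discards an observed primary event when its onset falls after discharge and the subject leaves before any contact on day 7 or later. For one affected subject the primary estimate is 6.7 points lower (0/14 instead of 1/15), or 6.2 points lower if there is one other event (1/14 instead of 2/15).

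These sizes assume 15 procedures, no repeat ablations and exactly one affected subject. The documents give no early-exit rate and identify no affected subject, so the realised effect may be nil. The rule should still be corrected: it governs the primary safety result of a first-in-human study with few expected events, and the correction is almost free.

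A related death after discharge and before day 7 would fall under the clause only if death is treated as study exit. The documents do not settle this, and the conclusion does not depend on it.

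**What to change.** In SAP 7.4, reword condition (B) so that a subject is missing only if they have no CEC-adjudicated primary endpoint event, as defined in 7.2.2, observed on or before study exit. Only event-free early exits are then set to missing.

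In the final report, state how many subjects were set to missing under 7.4, so that readers can bound what remains. For example, 1/14 with one subject missing lies between 1/15 = 6.7% and 2/15 = 13.3%.

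Record the change in SAP 7.8, which already allows a newer SAP version or a deviation explained in the final report.

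The cost is one clause, one reported count and one line in 7.8, with no new data. The sponsor can check at once whether any of the 15 subjects is affected. The downside is that inclusion of early exits still depends on outcome, which can raise the rate by about 0.5 to 1.0 point per event-free exit at 1 or 2 events.

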12.1. Primary Objective

Estimate the incidence of ArcticLine Catheter-related and ArcticLine cryoablation procedure-related serious adverse events (SAEs) with an onset date within 7 days post-procedure.

Endpoint Definition

ArcticLine Catheter-related or ArcticLine cryoablation procedure-related SAEs, with an onset date within 7 days post-procedure (except as noted below), as adjudicated by the Clinical Events Committee (CEC), described as follows:

- Atrioesophageal fistula*
 - * Includes atrioesophageal fistula with an onset date at any time after the study cryoablation procedure and is adjudicated by the CEC as either ArcticLine Catheter-related or ArcticLine cryoablation procedure-related.
- Cardiac perforation/tamponade
- Cerebrovascular accident
- Death
- Esophageal injury
- Major bleeding
- Myocardial infarction
- Pericarditis
- Phrenic nerve injury (ongoing at hospital discharge)
- Transient ischemic attack
- Vagal nerve injury resulting in esophageal dysmotility or gastroparesis
- Vascular access complications

Sample Size

The sample size of 15 treated subjects for this study was chosen with the goal to collect preliminary safety and effectiveness data on the ArcticLine Catheter's use in both the left and right atrium.

Analysis Methods

The percentage of catheter related and cryoablation procedure related SAEs will be calculated as the number of procedures with at least one SAE meeting the endpoint definition divided by the number of cryoablation procedures. Each procedure will count, so subjects with repeat cryoablations will contribute more than once to the denominator. Exact methods will be used to construct a 95% confidence interval for the percentage of procedures with an SAE.

Determination of Patients for Analysis

All ArcticLine cryoablation procedures will be included. An ArcticLine cryoablation procedure is considered to have occurred once the ArcticLine Catheter is introduced into the vasculature.

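### SAP 7.4 makes missingness for the primary endpoint depend on the observed outcome, so the 7-day SAE rate can be biased in either direction if a treated subject exits before the one-week contact

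*SAP*

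**What the plan says.** SAP 7.4 removes a subject from the primary analysis when two conditions both hold. The subject must "exit the study prior to completion of a phone conversation or follow-up visit 7 or more days after the index procedure", and those who also "do not have a primary safety event on or before discharge from the index ablation will be considered as missing". An early exit with a primary event by discharge is therefore kept and counted as an event. The paragraph goes on to rule out imputation, calls all analyses complete-case, and says that they "assume that observed missingness occurs completely at random with respect to the outcome".

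Three other places bear on this:

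- **Endpoint and estimator (SAP 7.2.2).** The endpoint covers SAEs "with an onset date within 7 days post-procedure (except as noted below"; the exception is atrioesophageal fistula, which counts at any time. The estimate is the "number of procedures with at least one SAE meeting the endpoint definition divided by the number of cryoablation procedures", with an exact 95% interval.
- **Denominator (Protocol 12.1, repeated in SAP 7.2.2).** "All ArcticLine cryoablation procedures will be included". Neither section makes an exception for early exit.
- **Data from exited subjects (Protocol 8.12).** "All data available through the time of the subject's exit will be used for analysis".

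SAP 7.8, which lists changes and additions relative to the protocol, does not mention the exclusion in 7.4.

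**The concern.** Take two treated subjects who leave the study on day 4. One had a tamponade before discharge and counts as one event in one procedure. The other had no event and disappears from the denominator. Being missing is thus decided partly by the outcome, which is the opposite of missing completely at random.

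A second gap lies in the cut-off. The second condition looks only as far as discharge, but the endpoint runs to day 7. A subject who has a primary event on day 3 after going home, and leaves before the one-week contact, meets both conditions and is set to missing. The event may well be on file: Protocol 8.12 asks for an unscheduled visit at early exit, and Protocol 8.8.4 includes an adverse event assessment in that visit.

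The primary result is one proportion from about 15 procedures, and treated subjects are not replaced (Protocol 5.1). One subject more or less is visible in the result, and the text gives two incompatible definitions of the denominator.

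**Working it through.** **Inputs from the documents.** N = 15 procedures and a planning rate of 1/15 = 6.7%, with a stated interval width of 32% (SAP 6). The interval is exact (Clopper-Pearson). SAP 7.2.2 notes that no repeat ablations have been or will be done, so procedures and subjects coincide.

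**Assumed.** The documents give no early-exit rate and no split of events before and after discharge. I use early-exit probabilities of 1/15, 2/15 and 3/15, and state the split each time.

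**Step 1: the plan's own figure.** The exact 95% interval for 1/15 is 0.17% to 31.95%. Its width is 31.8%, which rounds to the stated 32%.

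**Step 2: expected value under the rule.** Let p be the true 7-day rate, s the share of events that occur by discharge, d the early-exit probability for subjects without a post-discharge event, and e the early-exit probability after a post-discharge event.

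- Retained events: E = p·s + p·(1−s)·(1−e)
- Retained non-events: F = (1−p)·(1−d)
- The rule estimates E/(E+F).

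*Upward case: all events by discharge (s = 1), exit unrelated to outcome, p = 1/15.*

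| d | E/(E+F) | Result |
|---|---|---|
| 1/15 | 0.0667/(0.0667 + 0.8711) | 7.1% |
| 2/15 | 0.0667/(0.0667 + 0.8089) | 7.6% |
| 3/15 | 0.0667/(0.0667 + 0.7467) | 8.2% |

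*Neutral case: all events after discharge (s = 0), exit unrelated to outcome (e = d).* The factor (1−d) cancels and the result is p = 6.7%.

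*Downward case: half of events after discharge (s = 0.5), d = 1/15, exit linked to those events.* With e = 0.5: 0.0500/(0.0500 + 0.8711) = 5.4%. With e = 1: 0.0333/(0.0333 + 0.8711) = 3.7%.

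**Step 3: single data sets.**

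| Situation | All procedures, known events counted | SAP 7.4 as written |
|---|---|---|
| 1 event by discharge, 2 event-free early exits | 1/15 = 6.7% (0.2 to 31.9) | 1/13 = 7.7% (0.2 to 36.0) |
| No events, 2 early exits | 0/15 = 0% (upper 21.8) | 0/13 = 0% (upper 24.7) |
| 1 event after discharge within 7 days, that subject exits early | 1/15 = 6.7% (upper 31.9) | 0/14 = 0% (upper 23.2) |

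For zero events the upper limit is 1 − 0.025^(1/n).

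**Step 4: how much of the wider interval is due to outcome dependence.** In the upward case the mean upper limit over all possible data sets is 33.1%, 35.1% and 37.4% for d = 1/15, 2/15 and 3/15. Dropping every early exit whatever the outcome gives 32.6%, 34.1% and 35.8%; no losses gives 31.3%. Loss of N accounts for 1.3, 2.8 and 4.5 points, and the outcome-dependent part for about 0.5, 1.0 and 1.6 points.

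**The case against.** The best defence is that the rule follows the logic of a binary endpoint. A subject with at least one qualifying SAE has a settled outcome whatever happens later. A subject who leaves event-free does not, and so "will be considered as missing for the primary endpoint analysis, on grounds that the assessment of the endpoint is incomplete". On that view the complete-case label is defensible, and I accept it for events by discharge. It does not rescue the randomness assumption, because keeping settled events while dropping unsettled non-events is itself selection on the outcome. Nor does it cover an event between discharge and day 7, whose outcome is equally settled but is dropped.

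The protocol also leaves data-handling rules to the SAP (Protocol 12), so added detail is not in itself a conflict. That is fair, but a rule that removes procedures from a denominator stated to hold all of them is more than detail, and SAP 7.2.2 repeats the protocol's statement.

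The effect is small and contingent. The interim trigger in SAP 7.6 presupposes that 15 treated subjects had a one-week visit, and if so nothing changes. No hypothesis is tested, there is no predefined stopping criterion, and SAP 7.27 tabulates related SAEs for all ArcticLine-treated subjects. All of this stands and limits the weight of the point.

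A reader might infer that the rule always inflates the SAE rate and its upper limit. The documents do not support that. The cut-off is discharge, not exit, so the rule can also remove a known event and lower both figures, and with no events the rate stays at 0%. A reader might also infer that a related death after discharge would be dropped. SAP 7.4 does not say whether death counts as exit, and Protocol 12.6 lists the two separately, so this is unclear rather than established.

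**Conclusion.** The rule is wrong as written. Missingness depends on the outcome seen by discharge, contrary to the assumption stated in the same paragraph, and the denominator disagrees with Protocol 12.1, SAP 7.2.2 and Protocol 8.12. The direction of bias is not fixed: it depends on when events occur and on whether they lead to exit. The upward shift is modest, about 0.4 to 1.5 points in the expected rate at a true rate of 6.7% and assumed exit probabilities of 1/15 to 3/15. Most of the accompanying rise in the upper limit is loss of N. The downward case matters more for a safety endpoint, because a single discarded event takes the reported rate from 6.7% to 0%. Both cases require at least one treated subject to exit before a contact at day 7 or later, and the documents do not say that any did.

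**What to change.** Amend SAP 7.4 for the primary endpoint as follows:

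1. Count every adjudicated primary event through exit, whether before or after discharge.
2. Keep all ArcticLine procedures in the denominator.
3. If any event-free subject lacks a contact at day 7 or later, report x/15 labelled as a lower bound, beside a worst case that counts each such subject as an event. Give exact intervals for both. With one event and two such subjects these are 1/15 = 6.7% (0.2 to 31.9) and (1+2)/15 = 3/15 = 20.0% (4.3 to 48.1).
4. Delete the completely-at-random statement for this endpoint.
5. State that the two figures are bounds and not imputation, so that 7.4 stays consistent with the no-imputation statement in the protocol synopsis.
6. Say whether death counts as exit.

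The cost is a wording change and at most one extra line in the primary table. The downside is that the lower figure assumes no event between exit and day 7. That would bias a safety rate downward if shown alone, which is why both bounds are needed. SAP 7.4 already accepts a similar assumption for late fistula in subjects who leave after the one-week call.
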